7.3.4. Recurrent CDI

The following are study definitions for recurrent CDI.

7.3.4.1. Recurrent CDI for Study Entry

To be considered for enrollment, a subject must have medical record documentation of:

- a) a current diagnosis or history of recurrent CDI as determined by the treating physician,

b) or has had at least two episodes of severe CDI resulting in hospitalization.

7.3.4.2. Recurrent CDI On-study

1. The passage of three or more unformed/loose (i.e., Bristol Stool Scale type 6-7) stools in 24 or fewer consecutive hours for at least two consecutive days,
2. and a positive stool test for the presence of *C. difficile* as determined by the central laboratory.

7.3.5. Sustained Clinical Response

Sustained clinical response is defined as:

- Treatment success of the presenting CDI recurrence and no new CDI episodes through 6 months after completing a study treatment.

7.3.6. Treatment Failure

Treatment failure (CDI recurrence) is defined as:

- The presence of CDI diarrhea within 8 weeks of administration of a study enema, which includes a positive stool test for *C. difficile* as determined by the central laboratory.

7.3.7. Treatment Success

Treatment success is defined as:

- The absence of CDI diarrhea through 8 weeks after completing a study treatment.

7.4. Determination of Treatment Success/Failure

The site investigator makes the initial determination of treatment success or failure based on the pre-defined study definitions (**Section 7.3.1, 7.3.6, and 7.3.7**). The site investigator's assessment will then be provided to the Endpoint Adjudication Committee (EAC) for independent adjudication of treatment success or failure that will be utilized for study analysis and reporting purposes. This may be done on an on-going basis or a single meeting. Details of the EAC logistics, activity and responsibilities will be included in an EAC charter.

7.5. Management of Treatment Failure

Following treatment, subjects meeting the protocol definition of treatment failure (**Section 7.3.6**) may be scheduled for administration of a second RBX2660 enema within 21 calendar days of failure determination. To receive the second RBX2660 enema, the site must provide documentation of meeting all treatment failure criteria as defined in **Section 7.3.6**. If the definition of treatment failure is not met, a second study treatment of RBX2660 will not be provided.

Treatment failures are required to be entered in the study database shortly after determination of failure to allow for sponsor awareness and assurance that a second study treatment of RBX2660 can be provided if requested.

The use of antibiotics prior to a second RBX2660 enema is at the discretion of the investigator. If antibiotics are given to control symptoms, a 24-72 hour washout period prior to administration of a second RBX2660 enema is required. If the subject will have a second enema, it needs to be administered within 21 calendar days of failure determination.

If a subject receives a second RBX2660 enema, follow-up is completed via telephone assessments at 1-week, 4-weeks, 8-weeks, and 6 months after the second study treatment of RBX2660.

Treatment failures who do not receive a second RBX2660 enema will continue to follow their original schedule of assessments for the duration of the study based on the first study enema.

If a subject has a treatment failure after receiving a second study treatment of RBX2660, the subject should be treated per the investigator's discretion.

7.6. Medical Monitor

The Medical Monitor provides review of serious adverse events or events reported by the site as related to the investigational product or enema procedure to assess accuracy of reporting as related to seriousness and causality, and periodic review of adverse events for trends. Details of this review are documented in a Safety Management Plan. The Medical Monitor's review will be provided to the DSMB for analysis purposes and as applicable for the proper adjudication of potential study stopping rules.

7.7. Data and Safety Monitoring Board

The DSMB will review safety data for trends for the final analysis. Details regarding DSMB responsibilities related to analysis oversight, data reporting, and timing of meetings will be provided in the DSMB Charter.

7.8. Endpoint Adjudication Committee

The Endpoint Adjudication Committee (EAC) provides independent adjudication of treatment success or failure that will be used for study analysis and reporting purposes. Details of the EAC logistics, activity and responsibilities will be included in an EAC charter.

7.9. Bias

This is an open-label study with a single arm. The study is not blinded. Measures taken to minimize bias include selection of qualified investigators and study sites, adherence to the eligibility criteria (**Section 8**), and adherence to this protocol.

8. Subject Selection and Withdrawal

8.1. Inclusion Criteria

All responses must be “yes” to include a subject in the study:

1. ≥ 18 years old.
2. Medical record documentation of either a) a current diagnosis or history of recurrent CDI as determined by the treating physician, b) or has had at least two episodes of severe CDI resulting in hospitalization.
3. Is currently taking or was just prescribed antibiotics to control CDI related diarrhea at the time of enrollment. *Note: Subject's CDI diarrhea must be controlled (<3 unformed/loose, i.e., Bristol Stool Scale type 6-7, stools/day for the two consecutive days prior to the washout period) while taking antibiotics during screening.*
4. Willing and able to have an enema(s).
5. Willing and able to complete the stool and blood testing required for the study.
6. Agrees to not take non-dietary probiotics from Screening through 8 weeks after receiving the last study enema (including OTC and prescription).
7. Agrees to not take any oral vancomycin, metronidazole, fidaxomicin, rifaximin, nitazoxanide, bezlotoxumab, or IVIG through the 8-week follow-up assessment unless newly prescribed by a treating investigator during the course of the study as a result of recurrent CDI diagnosis. *Note: Use of IVIG for treatment of a non-CDI indication is allowed.*
8. Agrees to practice a form of effective contraception during study participation; does not apply to persons with documented non-child bearing potential.
9. Has a negative urine pregnancy test at the time of enrollment and on the day of each enema prior to administration (persons of child-bearing potential only).

10. Willing and able to provide informed consent, and local privacy authorization as applicable.
11. Willing and able to complete the required Subject Diary.
12. Willing and able to meet all study requirements, including attending all assessment visits and telephone calls.

8.2. Exclusion Criteria

All responses must be “no” to include a subject in the study:

1. A known history of refractory CDI.
2. Currently has continued CDI diarrhea despite being on a course of antibiotics prescribed for CDI treatment.
3. Requires systemic antibiotic therapy for a condition other than CDI.
4. Patient previously participated in a Rebiotix clinical study receiving RBX2660.
5. Fecal microbiota transplant (FMT) within the past 6 months.
6. FMT with an associated serious adverse event related to the FMT product or procedure.
7. Bezlotoxumab (CDI monoclonal antibodies) if received within the last year.
8. Disease symptoms (diarrhea) caused by a confirmed intestinal pathogen other than *C. difficile*.
9. Currently has a colostomy.
10. Intraabdominal surgery within the last 60 days. *Note: laparoscopic procedures that do not involve the GI tract are permitted.*
11. Planned surgery requiring perioperative antibiotics through the 8-week follow-up assessment.
12. Life expectancy of < 6 months.
13. CD4 count <200/mm³ during Screening.
14. An absolute neutrophil count of <1000 cells/µL during Screening.
15. Known or suspected current (< 90 days) illicit drug use. *Note: marijuana use is allowed.*
16. Pregnant, breastfeeding, or intends to become pregnant during study participation.
17. Participating in a clinical study of another investigational product (drug, device or other) and has not completed the required follow-up period.
18. Subject is eligible for another RBX2660 study.
19. Subject, in the opinion of the investigator, for whatever reason, should be excluded from the study.

8.3. Subject Recruitment and Screening

Subjects are recruited by qualified and trained site personnel when they are identified as recently diagnosed with or experiencing recurrent CDI or are experiencing at least a

second hospitalization due to CDI. Potential subjects are to be fully informed as to this study's purpose, requirements, anticipated risks, etc., and are to be given the chance to review the informed consent form and receive satisfactory answers to all questions. Subjects sign the study-specific, IRB/REB-approved Informed Consent and local privacy authorization (as applicable), which is the point at which the potential subject is considered enrolled in the study.

Subjects are eligible to receive study treatment upon confirmation that they have met all eligibility criteria listed in **Sections 8.1 and 8.2**. Antibiotics being taken for their recurrent CDI symptoms must stopped for a 24-72 hour washout period prior to receiving the study enema.

9. Investigational Product

9.1. RBX2660 Description

RBX2660 microbiota suspension 50 g/150 mL is supplied in an enema bag. Each bag of RBX2660 provides one enema. Each enema of RBX2660 consists of a suspension of minimum 10^7 live organisms/mL in polyethylene glycol 3350/0.9% Sodium Chloride Irrigation, USP, solution.

9.2. Rebiotix Kit Description

Investigational product is supplied in a single-enema bag fitted with a spike port and a rectal tube assembly that is used to administer IP as an enema; these components are packaged together in the Rebiotix Kit. Rebiotix Kit components include:

- 1 bag of RBX2660 with a spike port contained in a brown opaque sleeve
- 1 rectal tube assembly
- 1 biohazard disposal bag
- 1 Instructions for Use (IFU)

9.3. Treatment Regimen

Study treatment needs to be administered within 21 days of the Screening visit. Product is to only be administered by the authorized IP Administrator who must be a qualified and trained health care professional following the Instructions for Use and standard site procedures. Subjects are to remain at the site under supervision for at least one-hour post-enema administration for vital sign assessment (temperature, heart rate, blood pressure, respiratory rate) and observation.

Subjects with a documented treatment failure following treatment may be scheduled for administration of a second RBX2660 enema. In order to receive a second RBX2660 enema, a subject must have documentation of meeting all treatment failure criteria as defined by the protocol (**Section 7.3.6**).

If, in the opinion of the investigator, antibiotics are warranted for the control of CDI symptoms prior to receiving the second RBX2660 enema, they can be administered but need to be stopped 24-72 hours before enema administration. The total time from a treatment failure (CDI recurrence) determination to administration of a second enema is within 21 calendar days.

See **Section 10** for the Schedule of Study Procedures and detailed description of the requirements.

9.4. Subject Follow-up Requirements

Subjects are assessed at office visits at 1- and 8-weeks and via telephone calls at 4-weeks and at 4 and 6 months after the study enema. See **Section 10** for follow-up assessments and phone calls, and **Section 10.16** for subject withdrawal/termination.

9.5. Concomitant Therapy

The subject must agree to not take any oral vancomycin, metronidazole, fidaxomicin, rifaximin, nitazoxanide, bezlotoxumab, or IVIG through the 8-week follow-up assessment unless newly prescribed by a treating investigator during the course of the study as a result of recurrent CDI diagnosis. Use of IVIG for treatment of a non-CDI indication is allowed. Use of non-dietary probiotics from Screening through 8 weeks after receiving the last study enema (including OTC and prescription) is also prohibited.

Medication information will be collected at the Screening visit and changes in medications will be recorded throughout the study. Subjects should be encouraged to notify their general practitioners of study participation and the requirements for concomitant therapy.

9.6. Preparation of Investigational Product

Instructions for Use with detailed directions for IP preparation and administration are included in each Rebiotix Kit.

9.7. Packaging

Investigational product is supplied in an enema bag fitted with a spike port and a rectal tube assembly that is used to administer the product via enema; these components are packaged together in the Rebiotix Kit.

9.8. Ordering, Receipt and Storage, Dispensing, Returning, and Tracking Investigational Product

9.8.1. Ordering Investigational Product

Authorized site personnel will order IP through the study database. If a subject is a confirmed treatment failure and will proceed to a second RBX2660 treatment, the site will document the failure in the database, and complete a re-order form in the database to trigger a shipment of IP for the second RBX2660 treatment.

9.8.2. Receipt and Storage of Investigational Product

Note: Each unit of IP is designated to be administered to a specific subject on a specific date; administration of IP designated for one subject to another subject is prohibited.

IP is shipped to the authorized person/department as specified on the Delegation of Authority log at the site in a temperature-controlled shipping package. The authorized person opens the shipping package, visually confirms that the unit of IP arrived intact, confirms that the temperature indicator has not been tripped and records receipt and inspection on the Product Accountability Log. IP is to be thawed and stored in the refrigerator until administration.

IP must be kept in a secure location under the control of the Investigator or authorized designee at all times; see **Section 9.8.5** for details. IP must be administered to the subject by the expiration date as specified on the label. If it is not administered by the expiration date, it must be destroyed by site staff per the institution's processes and be recorded on the Product Accountability Log.

9.8.3. Dispensing and Administering Investigational Product

Dispensing procedures vary from site to site, but each site's study investigator is responsible for delegating the administration of IP to a qualified and trained health care professional; this person(s) ("IP Administrator") must be identified on the Delegation of Authority Log and receive product-specific training on IP administration.

IP is to be administered by the IP Administrator after all inclusion/exclusion criteria have been met, the subject had a negative pregnancy test (if applicable) and the 24-72 hour antibiotic washout period has been completed. Administration is via enema

following the Instructions for Use in each product package and the site's standard procedures.

9.8.4. Returning IP

Do not return IP to Rebiotix. IP received but not administered to a subject must be destroyed by site staff per the institution's processes. Destruction must be recorded on the Product Accountability Log.

9.8.5. Product Accountability and Tracking

Each unit of IP is sent to the site for administration to an assigned subject and is labeled with a batch number to be recorded in the electronic case report form (eCRF) and on the Product Accountability Log. Each unit must be tracked on the Product Accountability Log by the person(s) authorized on the Delegation of Authority Log to perform that step. IP must be kept in a secure location under the control of the site investigator or authorized designee as recorded on the Delegation of Authority Log. The Product Accountability Log and Delegation of Authority Log are to be maintained by the site and confirmed during monitoring visits. The steps to be tracked include dates of receipt and dispensing, batch number, subject number, storage in refrigerator, and destruction if not administered to a subject. The IP Administrator must ensure the correct batch number is administered to the correct subject.

10. Study Procedures

10.1. General Information

Study information is collected on study-specific eCRFs by the site. Study monitoring will occur at regular intervals to ensure the protection of subject rights and safety, data integrity and accuracy, and proper study conduct in compliance to the protocol and applicable regulations including 21 CFR 312 and ICH E6 GCPs. Study visits and telephone assessments must occur with the window specified in **Table 10-1**; visits and calls out of window or missed are to be reported as protocol deviations. The study-required procedures are to be conducted as shown in **Table 10-1**.

Timely and complete follow-up visits will ensure the scientific integrity of the data is maintained and allow for continued oversight of subject safety.

Table 10-1 Schedule of Events

Activity	Screening (Enrollment)	Baseline / Enema Administration (≤ 21 days from Screening)	Follow-up Visits: 1- and 8-Week (± 3 days) Assessments ¹	Follow-up Phone Assessment: Week 4 (± 3 days)	Follow-up Phone Assessment: 4 and 6 months (± 14 days)	Unscheduled Possible Recurrence Visit	Second Enema Administration ¹ (≤ 21 calendar days post Tx Failure)	Second Enema Follow-up Phone Assessment: 1-, 4-, and 8-weeks (± 3 days), and 6 months (± 14 days)
Informed consent obtained	X							
Demographics, medical history	X							
Prescribe/continue antibiotics for CDI symptom control	X							
Physical exam	X							
Stool sent to Rebiotix by subjects for testing and archiving (optional)	X		X	X	X	X		X
Central Lab CBC w/differential testing ³	X ³	X						
Central Lab CD4 testing	X ³							
Central Lab CMP & CRP testing	X							
C. difficile testing ⁴						X ⁴		
Central Lab stool and blood testing		X						
Urine pregnancy testing performed at site (if applicable)	X	X					X	
Cdiff32 Questionnaire	X		X		X	X		
Inclusion/exclusion criteria confirmed	X	X						
24-72hr washout period confirmed		X					X ⁷	
Enema administered		X					X	
Product complaint (if applicable)		X					X	
CDI symptoms assessed		X	X	X	X	X	X	X
Vital signs assessed	X	X				X	X	
Weight	X		X	X	X			X
Subject Diary discussed/reviewed	X	X	X ⁵					
Employment status assessed	X		X ⁶		X			
Concomitant medications	X	X	X	X	X	X	X	X
Adverse events assessed		X	X	X	X	X	X	X
Solicited events assessed ²		X	X ²					

¹ Documented treatment failures may receive a second RBX2660 enema.

² Solicited events are collected in the Subject Diary from the day of administration of the baseline enema until the day prior to the 1-week Follow-up visit. The Subject Diary is reviewed at the 1-week Follow-up visit. Solicited events that increase in severity from Screening should be assessed for a possible adverse event.

³ Exclusion criteria for absolute neutrophil count and CD4 should be assessed based on the blood samples collected at the Screening visit.

⁴ Tested at the central laboratory.

⁵ Subject Diary is reviewed only at the 1-week Follow-up visit.

⁶ Collected at the 8-week follow-up visit only.

⁷ If antibiotics were administered to manage CDI recurrence.

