In-office study follow-up visits will occur at weeks 1 and 8 after completing the Baseline visit. Telephone assessments will occur at week 4 and at months 4 and 6 after the Baseline visit. Subjects are required to keep a detailed diary to assess for solicited events from the date of Screening visit to the 1-week follow-up visit. The diary will be collected and reviewed at the Baseline visit prior to enema administration. The subject will continue to complete the diary for one week following the Baseline visit (enema administration) and it will be collected and reviewed at the 1-week follow-up visit.

Subjects may receive a second RBX2660 enema if they are deemed failures following treatment per the protocol-specified treatment failure definition (**Section 7.3.6**). This second enema is to be administered within 21 calendar days of failure determination. If a subject receives a second RBX2660 enema, the follow-up is completed via telephone assessments at 1-week, 8-weeks, and 6-months after completing the second enema. A final analysis and report will be completed once the last subject has completed the 6-month follow-up visit for their study treatment, including 6-month follow-up after a second RBX2660 study treatment, if applicable.

See **Figure 7-1** for an illustration of the Study Design.

[figure not shown]

Figure 7-1: Open-Label Study Design.

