10.3. Subject Diary

The Subject Diary serves as a tool for the subject to record pre- and post-treatment health and information. The Subject Diary is reviewed for solicited event occurrence and severity, changes to medications, occurrence of adverse events, and possible recurrence of CDI. The subject also documents changes in medications.

At the Screening visit, subjects are provided a Subject Diary to complete each day until the day prior to the study enema (Baseline visit). This may be up to 21 days. The diary will be reviewed at the Baseline visit prior to enema administration.

Prior to the subject leaving at the conclusion of the Baseline visit, the subject is instructed to continue completing the Subject Diary for each day until the 1-week office visit.

The following information is entered into the study database:

- solicited event severity
- changes to medication
- occurrence of adverse events

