5 BASELINE, SAFETY AND EFFICACY EVALUATIONS

5.1 Schedule of Events

Activity	Screening (Enrollment)	Baseline / Enema Administration (≤ 21 days from Screening)	Follow-up Visits: 1- and 8-Week (± 3 days) Assessments ¹	Follow-up Phone Assessment: Week 4 (± 3 days)	Follow-up Phone Assessment: 4 and 6 months (± 14 days)	Unscheduled Possible Recurrence Visit	Second Enema Administration ¹ (≤ 21 calendar days post Tx Failure)	Second Enema Follow-up Phone Assessment: 1-, 4-, and 8-week (± 3 days), and 6 months (± 14 days)
Informed consent obtained	X							
Demographics, medical history	X							
Prescribe/continue antibiotics for CDI symptom control	X							
Physical exam	X							
Stool sent to Rebiotix by subjects for testing and archiving (optional)	X		X	X	X	X		X
Central Lab CBC w/differential testing ³	X ³	X						
Central Lab CD4 testing	X ³							
Central Lab CMP & CRP testing	X							
C. difficile testing ⁴	X ⁴					X ⁴		
Central Lab stool and blood testing		X						
Urine pregnancy testing performed at site (if applicable)	X	X					X	
Cdiff32 Questionnaire	X	X	X		X	X		
Inclusion/exclusion criteria confirmed	X	X						
24-72hr washout period confirmed		X					X ⁷	
Enema administered		X					X	
Product complaint (if applicable)		X					X	
CDI symptoms assessed		X	X	X	X	X	X	X
Vital signs assessed	X	X				X	X	
Weight	X		X	X	X			X
Subject Diary discussed/reviewed	X	X	X ⁵					
Employment status assessed	X		X ⁶		X			
Concomitant medications	X	X	X	X	X	X	X	X
Adverse events assessed		X	X	X	X	X	X	X
Solicited events assessed ²		X	X ²					

¹ Documented treatment failures may receive a second RBX2660 enema.

² Solicited events are collected in the Subject Diary from the day of the baseline enema until the day prior to the 1-week Follow-up visit. The Subject Diary is reviewed at the 1-week Follow-up visit. Solicited events that increase in severity from Screening should be assessed for a possible adverse event.

³ Exclusion criteria for absolute neutrophil count and CD4 should be assessed based on the blood samples collected at the Screening visit.

⁴ Tested at the central laboratory

⁵ Subject Diary is reviewed only at the 1-week Follow-up visit.

⁶ Collected at the 8-week follow-up visit only.

⁷ If antibiotics were administered to manage CDI recurrence.

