5.2 Time Point Algorithms

5.2.1 *Relative Day*

The date of study enema administration will be considered relative day 1, and the day before study enema administration will be relative day -1. Relative days will be calculated as follows only when the full assessment date is known (i.e., partial dates will have missing relative days, unless imputation methods have been specified):

For days before first enema:

Date of Assessment – Date of first enema administration

For days on or after first enema:

Date of Assessment – Date of first enema administration +1

For the purpose of statistical analysis, the analysis visit windows will be calculated in terms of study days since the day of the study enema administration, as illustrated in the following tables:

Table 1. Analysis Windows for Clinical Visits

Visit	Scheduled Study Day	Visit Window in Protocol (Days)	Visit Window for Analysis (Days)
Screening Visit	-20 through -1	-20 through -1	-20 through -1
Baseline/1 st Enema	1	1	1
1-week Office	8	5 - 11	5 - 11
8-weeks Office	57	54 - 60	54 - 60

Table 2. Analysis Windows for Phone Assessments

Visit	Scheduled Study Day	Visit Window in Protocol (Days)	Visit Window for Analysis (Days)
4-weeks - Phone	29	26 - 32	26 - 32
4 months - Phone	121	106 – 134	106 – 134
6 months - Phone	181	166 – 194	166 – 194

Table 3. Analysis Windows for Adverse Event Reporting by Onset Interval

Onset Interval Name	Onset Interval Analysis Window	Window for Analysis (Days)
Baseline	Screening - < Baseline	≤ -1
1-week	Baseline - 1-week	1 through 8
4-week	> 1-week - 4-week	9 through 29
8-week	> 4-week - 8-week	30 through 57
0-8-week	Baseline - 8-week	1 through 57
4-month	> 8-week - 4-month	58 through 121
6-month	> 4-month - 6-month	122 through 180+
8-week-6-month	> 8-week - 6-month	58 through 180+

If a subject has more than one assessment occurring in the same visit window, the data from the visit closest to the scheduled study day will be used for analysis. If two visits have the same distance from the scheduled study day, i.e., one visit occurs -1 day from study day, and the other visit occurs +1 day from study day, the data from the visit after the scheduled study day will be used for analysis.

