5.4.3.4 Treatment-Emergent Adverse Events

Adverse events will be considered treatment-emergent adverse events (TEAE) according to the following algorithm:

- If the complete onset date of an AE is known, then:
 - If AE onset date is prior to initial treatment date, then the AE will not be considered treatment-emergent.

- If AE onset date occurs after IP exposure on or after initial treatment date, then the AE will be considered treatment-emergent.
 - If AE onset date is partially known, then:
 - If day is unknown, and month/year occurs on or after first enema month/year, then AE will be considered treatment-emergent. Otherwise, AE will not be considered treatment-emergent.
 - If month/day is unknown, and year occurs on or after first enema year, then AE will be considered treatment-emergent. Otherwise, AE will not be considered treatment-emergent.

5.4.4 *Other Observations Related to Safety*

5.4.4.1 *Solicited Adverse Events*

The following list of anticipated adverse events are solicited from subjects via the Subject Diary from the date of enrollment through the 7th day after receiving the study treatment.:

- gas (flatulence)
- abdominal distension or bloating
- rectal irritation or pain
- chills/severe shivering
- abdominal pain or cramping
- increased diarrhea
- constipation
- rectal bleeding
- nausea
- vomiting
- fever $\geq 37.8^{\circ}\text{C}$ ($\geq 100.0^{\circ}\text{F}$)

Frequency and severity of the solicited AEs will also be captured in the Subject Diary.

5.4.4.2 *Major Complications of CDI Events*

Frequencies of major complications of CDI including death, septic shock, toxic megacolon, colonic perforation, emergency colectomy, or ICU admission will be collected through the 6-month telephone assessment after the last study enema.

5.4.4.3 *Hospitalizations for Recurrent CDI*

Details regarding hospitalizations due to CDI, including admission and discharge date/time, reason for admission, whether the subject was admitted to an ICU, and ICU admission and discharge date/time (if applicable), will be collected following both the first and second study enemas

5.5 **Efficacy Variables**

5.5.1 ***Efficacy Endpoint***

Assessment of secondary objectives will include descriptive statistics and be performed on pre-defined analysis populations including Intent-to-Treat (ITT), modified Intent-to-Treat (mITT) and Per-Protocol (PP). Additional sub-analyses of safety data may be performed on sub-populations.

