6.6.2.5 Subject Diary including Solicited Adverse Events and Completion Compliance

All solicited adverse events recorded in the Subject Diary will be summarized utilizing frequencies (number of events), proportions (number of subjects with the event) and 95% CIs for categorical variables and using the descriptive statistics as listed in **Section 8.1** for continuous variables.

For each solicited event, severity scores will be summarized as both categorical and continuous values. For continuous summaries, severity scores will be identified as either pre-treatment or post-treatment (all diary entries captured after the first enema), and the average for each period will be calculated across individual subjects. Baseline for continuous summaries will be considered the average during the pre-treatment period. For categorical summaries, if a subject reports more than one severity score on the same date, the maximum severity will be used. Baseline for categorical summaries will be considered the last non-missing assessment prior to the enema.

For each categorical summary of event frequency, a two-sided 95% CI will be calculated using the normal approximation of the binomial.

The following summaries will be produced for the first enema:

- Frequency of severity scores on day of enema administration
- Frequency of severity scores on day 1 through 1-week post-treatment
- Frequency of maximum post-treatment severity score

Compliance in returning completed Subject Diaries will be calculated by dividing the number of diaries turned in, whether complete or not, by the number of diaries expected to be turned in. Furthermore, compliance will be summarized by calculating the proportion of subjects who turned in “complete” diaries, where complete is defined as answering all 14 daily questions (e.g.

11 solicited AE, Bristol Stool Type, New illnesses/injuries, New medications) for at least 80% of the expected number of diaries.

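### The plan gives the solicited-event diary two different end points, so diary length follows the date of the 1-week visit and two SAP diary summaries inherit that dependence

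*Protocol*

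**What the plan says.** **Visit-dependent end.** Table 10-1 footnote 2 (Protocol 10.1) collects solicited events in the diary "from the day of administration of the baseline enema until the day prior to the 1-week Follow-up visit". Protocol 10.3 tells the subject to "continue completing the Subject Diary for each day until the 1-week office visit". The footnote under the SAP's schedule (SAP 5.1) agrees: "from the day of the baseline enema until the day prior to the 1-week Follow-up visit".

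**Fixed end.** SAP 5.4.4.1 says events are solicited "from the date of enrollment through the 7th day after receiving the study treatment". The protocol synopsis, Protocol 7.2 and SAP 3.1 have the diary continue for one week after Baseline, and also have it collected at the 1-week visit.

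**Visit window.** Table 10-1 allows ±3 days. SAP 5.2.1 states that "The date of study enema administration will be considered relative day 1", and SAP Table 1 schedules the 1-week visit on day 8 with a window of days 5 to 11.

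**Analysis.** SAP 6.6.2.5 plans three severity frequency summaries: the enema day, day 1 through 1 week, and the maximum after treatment. Only the last has no end day. For the continuous summaries the later period is "post-treatment (all diary entries captured after the first enema", again with no last day. A diary set is complete if all daily questions are answered for at least 80% of the expected diaries, but the expected number is not defined.

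**The concern.** Safety and tolerability are the primary objective, and the diary is the instrument that asks about eleven named symptoms day by day. If its length varies with the visit date, whether a subject is ever recorded at a given severity depends partly on how long anyone was asking. An early visit cuts the record short, and a late one adds days outside the period the SAP says it covers. The table of maximum severity would then mix subjects with different observation times under one label. Comparison with the sponsor's first Phase 2 study would also be weakened, because Protocol 5.3.1 describes a common 8-day period there, from the day of dosing through the seventh day after.

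**Working it through.** **1. Reproduce the visit window.** Scheduled day 8 (SAP Table 1), tolerance ±3 days (Table 10-1): 8 − 3 = 5 and 8 + 3 = 11. This matches the SAP's days 5 to 11.

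**2. Count diary days under footnote 2.** The diary runs from day 1 to the day before the visit, so diary days = visit day − 1. The 7th day after treatment is 1 + 7 = study day 8, so SAP 5.4.4.1 implies 8 diary days.

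| Visit day | Diary days | Against the SAP's 8 |
|---|---|---|
| 5 | 4 | −4 |
| 6 | 5 | −3 |
| 7 | 6 | −2 |
| 8 (on schedule) | 7 | −1 |
| 9 | 8 | 0 |
| 10 | 9 | +1 |
| 11 | 10 | +2 |

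The range is 10 / 4 = 2.5-fold. Of the seven permitted visit days, only day 9 gives the stated period.

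**3. Effect on the maximum.** The documents give no daily rates for this population, so the size can only be illustrated. Let h be the chance of a given severity being recorded on the enema day, and let it be multiplied by r on each later day. The chance of at least one such entry in k days is 1 − ∏(1 − h·rⁱ), for i = 0 to k − 1. I set h so that the 7-day chance equals an assumed value.

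Worked case, 7-day risk 20%, r = 1: h = 1 − 0.8^(1/7) = 0.0314. Four days give 1 − 0.8^(4/7) = 12.0%, and ten days give 1 − 0.8^(10/7) = 27.3%. For r = 0.75, h = 0.0630; for r = 0.5, h = 0.1083.

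| Assumed 7-day risk | Constant (r = 1), 4 vs 10 days | Falling 25% a day (r = 0.75) | Halving daily (r = 0.5) |
|---|---|---|---|
| 5% | 2.9% vs 7.1% | 4.0% vs 5.4% | 4.7% vs 5.0% |
| 20% | 12.0% vs 27.3% | 16.2% vs 21.5% | 19.0% vs 20.1% |
| 40% | 25.3% vs 51.8% | 33.4% vs 42.6% | 38.4% vs 40.2% |

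Protocol 5.3.1 reports that the incidence and severity of solicited events declined over the 8 days, which favours the right-hand columns.

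**4. Effect on the average.** An average does not rise mechanically with days. If severity declines, a 4-day average sits higher than a 10-day one, so the average and the maximum can move in opposite directions.

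**5. Effect on compliance.** Counting post-treatment entries only, a subject seen on day 7 who fills every page has 6 of 6 = 100% if the visit date sets the expected number, but 6 of 8 = 75%, below the 80% limit, if SAP 5.4.4.1 does.

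**The case against.** The strongest reply is that little hangs on this.

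- **The primary endpoint is a different measure.** It counts subjects with related treatment-emergent adverse events, and adverse events are assessed at every later contact. A symptom that appears after an early visit can still be reported at the 4-week call. A reader might infer that the primary result is distorted; the documents do not support that. The study is single-arm and descriptive, with no between-arm contrast to bias.
- **A large effect is not shown.** Constant daily risk is the least favourable case for the plan and sits badly with the reported decline.
- **The Day-7 figure does not rescue it.** In the first Phase 2 study 51.5% (17/33) still reported solicited events on Day 7 after one treatment. A reader might take this as proof that the lost days carry new, worse events. It is the prevalence of any event at any severity, and only a new higher grade raises a maximum.
- **Ill subjects being seen early is conjecture.** Suspected recurrence has its own unscheduled visit, and no distribution of visit days is given.
- **The ten-day end depends on the reading.** The one-week wording would cap late diaries, so it rests on footnote 2 and Protocol 10.3.
- **One summary is already bounded,** namely day 1 through 1 week.

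All of this stands, and it limits the size. It does not remove the conflict. Because the diary is collected at the visit, a subject seen on day 5 does not reach the 7th day under any of the wordings. Under footnote 2, neither does a subject seen exactly on time.

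**Conclusion.** The defect holds in a limited form. It is not simply the protocol against the SAP: SAP 5.1 and SAP 5.4.4.1 contradict each other. Followed exactly, the plan yields 4 to 10 diary days against a stated 8, and 7 for an on-time visit. The maximum-severity and post-treatment-average summaries therefore depend on visit timing, and diary compliance has no defined denominator.

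For the maximum, the direction is certain. The size is unknown: at an assumed 7-day risk of 20%, the gap between the extremes runs from 1.1 percentage points (20.1 − 19.0, risk halving daily) to 15.3 (27.3 − 12.0, constant risk), and the reported decline points to the lower part. These are comparisons between the two ends of the window, so the effect on the pooled table will be smaller if most visits fall near day 8. The consequence is confined to the descriptive diary tolerability and compliance tables.

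**What to change.** Reconcile the statements to one window: enema day through the 7th day after it, study days 1 to 8. This is already the 1-week adverse-event interval in SAP Table 3 and matches the first Phase 2 study.

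- **Collection.** Amend Table 10-1 footnote 2, Protocol 10.3, the one-week wording in the synopsis, Protocol 7.2 and SAP 3.1, and the SAP schedule footnote, so that the diary runs to that day whatever the visit date. Pages outstanding at the visit are returned by mail or read out at a call.
- **Analysis.** In SAP 6.6.2.5, limit maximum severity, post-treatment averages and the expected post-treatment diary count to days 1 to 8. Later entries go to listings only.

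Both parts are needed. Truncating the analysis removes the late excess but cannot recover days lost to an early visit. For subjects whose diaries are already closed, apply the analysis window and report how many diary days each contributed.

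**Cost.** This needs a protocol and SAP amendment, with the approvals in Protocol 13.14, and a small new retrieval step at about 80 sites. A subject seen on day v, for v from 5 to 8, owes 9 − v further entries: four at most, and one after an on-time visit. Some of those pages will not come back.
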